## 4.0 Summary of Study Design

This multicenter, Phase 1b/2 study will investigate the safety, PK, PD and make a preliminary assessment of the anti-leukemic activity of the selective, 3rd generation SYK inhibitor, LANRA, in combination with the selective FLT3 inhibitor, gilteritinib, in patients with *FLT3*-mutated AML, who have recurrence of leukemia or are refractory after at least 1 prior regimen. This study will be conducted in 2 parts: dose escalation (Phase 1b) and cohort expansion (Phase 2). The study will consist of a Screening Phase lasting up to 21 days during which patients will be assessed for eligibility; a Treatment Phase beginning on Cycle 1, Day 1 (C1D1) consisting of consecutive 28-day cycles; an End-of-Treatment evaluation; and a Post-Treatment Follow-up Phase. During the Treatment Phase, patients will undergo study visits on Days 1, 2, 4, 8, 11, 15, 16 and 22 in Cycle 1, Days 1, 8, 15 and 22 in Cycle 2, and Days 1 and 15 in Cycle 3 and beyond. Approximately 100 patients are estimated to enroll across both Phase 1b and Phase 2; patients will be enrolled from multiple trial sites worldwide. In both Phase 1b and Phase 2, patients will receive their assigned treatment regimen until progression/relapse or lack of at least a PR after 6 months of study treatment, intolerance, or withdrawal from study treatment by the patient or study investigator. All patients will be followed for survival.

### 4.1 Phase 1b

Eligible patients will be enrolled sequentially into dose cohorts listed in Table 1 for PK/PD evaluations and determination of the MTD/RP2D of LANRA in combination with gilteritinib.

**Table 1: Dose-escalation Scheme (Provisional)**

Dose Cohort (n):	LANRA Dose:	Gilteritinib Dose:
Cohort 1	20 mg QD	120 mg QD
Cohort 2	40 mg QD	120 mg QD
Cohort 3	60 mg QD	120 mg QD
Cohort 4	90 mg QD	120 mg QD

A “3 + 3” dose escalation scheme will be employed in which 1 DLT reported from among the first 3 evaluable patients in a dose cohort will prompt enrollment of 3 additional evaluable patients. More than 1 DLT attributed to LANRA among 6 patients evaluable for DLT would indicate an intolerable dose, thus rendering the most proximate lower dose with either 0 of 3 or 1 of 6 patients with LANRA-related DLTs the MTD. Dose-limiting toxicities are defined in [Appendix 1](#). The starting dose of LANRA is 20 mg QD (Cohort 1, Table 1). Enrollment will be staggered such that the first patient to enroll in a dose cohort will begin combination therapy on C1D2 (see below) and at least 24 hours before subsequent patients are enrolled to that cohort. All patients within a cohort (except those who discontinue in Cycle 1 due to DLT) must complete the DLT assessment period before a decision to begin testing the next higher dose. Enrollment of the next higher dose cohort will not proceed until a safety review has been completed for the preceding cohort(s) by a DEC consisting of

investigators with enrolled patients and sponsor representatives including (but not limited to) the medical monitor, safety officer, PK, and translational science leads. All decisions regarding dose escalation including declaration of the MTD/RP2D will be made by the DEC. The determination of whether or not to enroll the next higher dose cohort, enroll a lower dose cohort/add additional patients to a cohort previously cleared for safety/tolerability by the DEC or declare the MTD/RP2D will be based on available safety, PK, and PD data from all dose cohorts. If no protocol-defined MTD is identified for LANRA, the lowest dose that shows consistent evidence of adequate SYK inhibition based on PD assays will be deemed the RP2D ([Section 2.6](#)).

Patients will be evaluated for DLTs beginning on C1D1 up to and including safety assessments collected on Cycle 2, Day 1 for determination of LANRA MTD in combination with standard-dose gilteritinib. Patients will be evaluable for DLT in Phase 1b if one of the following occurs:

- They experience a DLT after receiving  $\geq 1$  dose of LANRA during the DLT assessment period.
- They receive at least 80% of the intended cumulative dose of LANRA and gilteritinib during the DLT assessment period without the occurrence of a DLT.

Should patients discontinue study treatment prior to completing the DLT assessment period for reasons other than a DLT, additional patients will be enrolled to ensure the required number of DLT-evaluable patients is achieved. To better understand the safety, tolerability, PK, PD, and anti-tumor activity of the study regimen, additional patients (up to a total of 20 per dose cohort) may be allocated to previously cleared dose cohort(s) that are considered safe and adequately tolerated, if there are no available patient slots in the dose level currently being evaluated. The decision to enroll additional patients at a dose level previously cleared by the DEC (ie, enrollment of a “backfill” cohort) will be based on recommendations provided by the DEC coincident with each scheduled DEC convocation. Furthermore, additional patients may be added to a previously cleared dose cohort *only* if at least 1 of the 3 to 6 patients initially enrolled to that cohort have achieved one of the following ELN 2017-defined response categories ([Appendix 2](#)): CR, CRh, CRi, PR, MLFS. The 3+3 dose escalation rule will continue to be followed for each successively higher dose cohorts however, DLTs occurring in patients enrolled to backfill cohorts will be taken into account by the DEC for purposes of future dose escalation-making decisions, per guidelines outlined in [Section 2.6](#).

PK and PD evaluations of LANRA monotherapy will begin at Hour 0 (predose) on C1D1 through Hour 24 (C1D2) after which, all patients will initiate combination therapy on C1D2. PK evaluations for concurrently administered LANRA and gilteritinib will begin at Hour 0 (predose), C1D15 through Hour 24 (C1D16) (see [Table 8](#) and [Table 9](#)).

Patients who discontinue LANRA for intolerance may continue gilteritinib at the investigator’s discretion (in which case, no additional sampling for LANRA PK assessments will be required). Patients who discontinue gilteritinib for intolerance may continue LANRA at the investigator’s discretion for as long as they are deriving clinical benefit. An

End-of-Treatment evaluation will take place 30 ( $\pm$  7) days after permanent discontinuation of both study drugs or prior to initiation of new anti-leukemic therapy, if sooner. Patients who discontinue study treatment for reasons other than progression/relapse may be followed until progression in the absence of intervening antileukemic therapy, at the discretion of the investigator.

## 4.2 Phase 2

Following completion of Phase 1b, an expansion cohort consisting of patients who meet all eligibility criteria will enroll in order to further assess the safety, PK, PD (Table 10), and anti-leukemic activity of the combination at the LANRA MTD/RP2D. Patients enrolled to Phase 2 will begin combination therapy with LANRA and gilteritinib on C1D1.

For both Phase 1b and Phase 2, response assessments will be based on bone marrow, physical examinations, as well as peripheral blood counts. Bone marrow aspirates will be performed on C2D1, C3D1 and every 3 cycles thereafter until the patient exhibits 2 consecutive assessments indicating CR or CRh. Patients who have not achieved at least a partial response per ELN 2017 criteria after 6 months of study treatment will permanently discontinue study treatment.

Enrollment in Phase 2 will follow a two-stage design for assessment of the primary efficacy endpoint, composite CR (cCR) rate, including those patients who achieve a best response of CR or CRh, as defined by ELN 2017 response criteria (Appendix 2). Section 15.0 [Statistical Considerations] describes the specifications for enrollment in Stage 1 and Stage 2 based upon the hypothesized improvement in cCR rate resulting from the addition of LANRA to gilteritinib.

As in Phase 1b, the frequency of DLTs will be assessed coincident with the first cycle of treatment during Phase 2, initially after the first 6 patients and every patient thereafter, until enrollment completion. If the probability that the true, first cycle DLT rate exceeds 20% with 80% posterior probability given the accumulated data at these time points, further enrollment will be interrupted, and the DEC will be convened to assess the risk-benefit profile of the study regimen and provide recommendations regarding modifying or stopping the study (see Section 15.2.7.1 for safety stopping rules). Additionally, the occurrence of one Grade 5 event or two Grade 4 events that is considered at least possibly related to LANRA or gilteritinib will prompt an interruption of new patient accrual followed by a thorough safety analysis that will be submitted to health authorities in the countries where the study is being conducted for review prior to resuming enrollment.

## 5.0 Patient Population

### 5.1 Inclusion Criteria

Participants are eligible to be included in the study only if all the following criteria apply:

1. Adults  $\geq 18$  years of age with AML and at least 1 prior line of therapy.

**Note:** Patients must meet the criteria for a partial response, stable disease or progressive disease as best response after the last prior line of therapy; primary refractory disease after 1st line induction; or recurrence of leukemia after CR, as defined by ELN 2017 response criteria ([Appendix 2](#)).

2. *FLT3*-mutated disease documented in a local reference laboratory at the time of consideration for enrollment in the study.

**Note:** Eligible patients may have either ITD or TKD mutations or both as detected in either peripheral blood or bone marrow.

**Note:** Patients with a history of exposure to midostaurin, other multikinase inhibitor (eg, sorafenib), or 2nd generation *FLT3* inhibitors (including gilteritinib, quizartinib, or crenolanib) for the treatment of AML are eligible but must have discontinued treatment with these agents at least 7 days prior to Cycle 1, Day 1.

3. Have the ability to understand the requirements and procedures of the study and sign a written informed consent form (ICF).
4. Eastern Cooperative Oncology Group (ECOG) performance status (PS) of 0, 1 or 2.
5. Adequate hepatic and renal function defined as:
  - a) serum AST and ALT  $< 2.5$  times the upper limit of normal (ULN); total bilirubin  $< 1.5$  times ULN unless elevated due to Gilbert's Disease or hemolysis
  - b) calculated creatinine clearance  $> 30$  ml/min
6. Prothrombin time (PT), activated partial thromboplastin time (aPTT) and international normalized ratio (INR)  $\leq 1.5$ x ULN unless receiving therapeutic anticoagulation.

**Note:** Transition from a Vitamin K or Factor Xa antagonist to a low-molecular weight heparin preparation is recommended prior to the start of study treatment (see [Appendix 7](#) for guidelines on anticoagulation management).

7. Negative serum  $\beta$ -HCG test in women of child-bearing potential (WOCBP).
8. Left ventricular ejection fraction  $\geq 50\%$  confirmed by echocardiogram (ECHO) or multi-gated acquisition (MUGA) scan.
9. For WOCBP, willingness to abstain from heterosexual intercourse OR use a protocol-recommended method of contraception from 7 days prior to C1D1 throughout the study treatment period and for 6 months following the last dose of study treatment ([Appendix 6](#)).

10. For male patients with female sexual partners of childbearing potential, willingness to abstain from heterosexual intercourse OR use a protocol recommended method of contraception beginning 7 days prior to C1D1 throughout the study treatment period and for 4 months following the last dose of study treatment AND to refrain from sperm donation from the start of study treatment throughout the study treatment period and for 4 months following the last dose of study treatment ([Appendix 6](#)).
11. Willingness to comply with scheduled study visits, procedures, and treatment plan.

## 5.2 Exclusion Criteria

Participants are excluded from the study if any of the following criteria apply:

1. Known central nervous system (CNS) involvement with leukemia.
2. Clinical signs/symptoms of leukostasis that have failed therapy including hydroxyurea and/or leukapheresis of at least 3 days duration (see Exclusion Criterion #14 below).
3. Pregnant or breastfeeding women.
4. Active infection with hepatitis B, C or human immunodeficiency virus (HIV) infection.

**Note:** Patients who are hepatitis B surface antigen (HBsAg) or anti-HIV positive at baseline are ineligible. Patients with a history of hepatitis B virus (HBV) infection (hepatitis B antibody [anti-HBc] seropositivity) must agree to receive HBV prophylaxis during the study treatment period and undergo regular surveillance for HBV reactivation with serial HBV DNA measurements in plasma. Patients with a history of hepatitis C virus (HCV) infection who completed curative therapy may enroll but must undergo regular surveillance monitoring for HCV reactivation.

5. Disseminated intravascular coagulation with active bleeding or signs of thrombosis.
6. Known active COVID-19 either symptomatic or asymptomatic, as determined by nasopharyngeal swab for severe acute respiratory syndrome (SARS) coronavirus 2 (SARS CoV-2) RNA or antigen.

**Note:** In the absence of signs, symptoms or physical findings suggestive of COVID-19, testing for SARS CoV-2 infection is not required for eligibility. Patients with a history of SARS-CoV-2 nasopharyngeal carriage (either with or without symptoms), who have subsequently tested negative on follow-up nasopharyngeal swab and are without signs or symptoms of COVID-19 may enroll. Patients who have been vaccinated against SARS-CoV-2 at least 2 weeks prior to the start of study treatment may enroll. Patients without contraindications, may be vaccinated against COVID-19 while on study, preferably upon completion of the DLT assessment period (Cycle 1).

7. Administration of a live attenuated virus vaccine within 35 days before C1D1.
8. History of non-myeloid malignancy *except* for the following: adequately treated localized basal cell, or squamous cell carcinoma of the skin, or localized melanoma

(with TNM stage either Tis [melanoma in-situ] or T1aN0M0) with complete resection; cervical carcinoma in situ; superficial bladder cancer; asymptomatic prostate cancer without known metastatic disease, with no requirement for therapy or requiring only hormonal therapy and with normal prostate specific antigen for > 1 year prior to start of study therapy; or any other cancer that has been in complete remission without treatment for  $\geq 3$  years prior to enrollment.

**Note:** Patients who are on adjuvant hormonal therapy and  $\geq 3$  years from definitive therapy for their primary tumor are eligible to enroll.

9. Clinically significant heart disease defined as:
  - a) New York Heart Association Class 3 or 4 congestive heart failure,
  - b) Acute myocardial infarction  $\leq 6$  months before enrollment,
  - c) Symptomatic cardiac ischemia/unstable angina  $\leq 3$  months before enrollment,
  - d) History of clinically significant arrhythmias (eg, ventricular tachycardia or fibrillation; Torsades de Pointes) including Mobitz type II 2nd degree or 3rd degree heart block without a permanent pacemaker in place.
10. Patients with a corrected QT interval (using the Fridericia formula, QTcF) >480 msec or Long QT Syndrome.
11. Evidence of ongoing *uncontrolled* systemic bacterial, fungal, or viral infection at the time of study treatment initiation.

**Note:** “Uncontrolled” infection would include (but is not limited to) persistence of fever or positive cultures in the setting of appropriate antimicrobial coverage.
12. Current (within 30 days of study enrollment) drug-induced liver injury, chronic active hepatitis, alcoholic liver disease, nonalcoholic steatohepatitis, primary biliary cholangitis with inadequate response to ursodeoxycholic acid or other health authority approved therapy, extrahepatic obstruction caused by cholelithiasis, cirrhosis of the liver, or portal hypertension.
13. Ongoing (within 6 weeks of study enrollment) hepatic encephalopathy.
14. Alcohol or drug addiction as determined by investigator.
15. Ongoing immunosuppressive therapy, including systemic chemotherapy for treatment of leukemia.

**Note:** Patients may receive hydroxyurea or leukapheresis for treatment of hyperleukocytosis until signs/symptoms and/or the risk of complications from leukostasis have abated, in the judgement of the investigator.

**Note:** Patients with a history of hematopoietic stem cell transplantation (HSCT) are eligible as long as they are receiving no more than 10 mg prednisone QD (or equivalent) for graft vs. host disease.
16. Concurrent (within 14 days of study enrollment) participation in an investigational drug study with therapeutic intent.

17. Patient requiring chronic treatment with strong cytochrome P450 (CYP) 3A4 inhibitors or inducers beginning 7 days prior to initiating study treatment until study treatment completion (see [Appendix 4](#) for a list of strong CYP3A inducers or inhibitors; see [Section 10.2](#) for LANRA treatment modification guidelines for patients requiring the use of strong CYP3A4 inhibitors during the Treatment Phase).
18. Unable to swallow capsules or concurrent disease affecting gastrointestinal function such as malabsorption syndrome, gastric or small bowel resection, bariatric surgery, inflammatory bowel disease or bowel obstruction.
19. Any prior or ongoing condition that, in the opinion of the investigator, could adversely affect the safety of the patient or impair the assessment of study results.
20. Known hypersensitivity to LANRA, gilteritinib, their metabolites or formulation excipient.

## **6.0 Organizational Framework**

### **6.1 Screening and Enrollment**

After signing the ICF, all screening assessments and procedures must be completed within 21 days before the start of study treatment. The study site is responsible for maintaining a record of all screened and enrolled patients. Patients who have failed 1 or more screening assessment may be re-tested for that assessment(s) within the designated time frame for final eligibility determination.

### **6.2 Treatment Phase**

The treatment period starts with the first day of study treatment (C1D1) and continues until the End-of-Treatment Evaluation (see below). All treatment cycles are 28 days. Patients may discontinue study treatment at any time for reasons summarized in [Section 13.0](#).

### **6.3 End of Treatment**

All patients will undergo an End-of-Treatment Evaluation  $30 \pm 7$  days after the last dose of either LANRA or gilteritinib (whichever is later) or prior to initiation of new antileukemic therapy, if sooner. Patients must discontinue study treatment and complete the End-of-Treatment Evaluation prior to HSCT.

### **6.4 Post-treatment Follow-up**

Patients who discontinue study treatment for reasons other than progression/relapse will be followed monthly until progression/relapse at the discretion of the investigator and in the absence of intervening new anti-leukemic therapy. Following progression/relapse or initiation of new anti-leukemic therapy, patients will be followed for survival every 3 months.

### **6.5 End of Study**

The study will end after all enrolled patients either relapse or die or 5 years after the last patient enrolls (whichever is earlier) or if the Sponsor decides to terminate the trial.

## 7.0 Test product, dose, mode of administration

### 7.1 Gilteritinib:

Gilteritinib (**XOSPATA®**) is supplied as light yellow, round-shaped, film-coated tablets debossed with the Astellas logo and '235' on the same side. Gilteritinib is provided in either bottles of 90 tablets with child resistant closure or a carton containing 4 blister strips of 21 tablets each for a total of 84 tablets. Each tablet contains 40 mg gilteritinib as well as the following commonly used excipients: ferric oxide, hydroxypropyl cellulose, hypromellose, low-substituted hydroxypropyl cellulose, mannitol, magnesium stearate, talc, polyethylene glycol and titanium dioxide. Store gilteritinib tablets at 20°C to 25°C (68°F to 77°F); excursions between 15°C to 30°C (59°F to 86°F) are permitted. Keep in the original container until dispensed and protect from light, moisture and humidity.

Do not break or crush gilteritinib tablets. Administer gilteritinib orally about the same time each day. If a dose of gilteritinib is missed or not taken at the usual time, administer the dose as soon as possible on the same day, and at least 12 hours prior to the next scheduled dose. Return to the normal schedule the following day. Do not administer 2 doses within 12 hours. Gilteritinib may be taken in either the fed or fasted state either with or without gastric acid reducing agents, including proton pump inhibitors (PPIs).

### 7.2 LANRA:

LANRA is available as biconvex, blue film-coated tablets. Each tablet contains 10 mg or 30 mg of LANRA free base as the succinate form. LANRA tablets contain commonly used excipients, including microcrystalline cellulose, mannitol, croscarmellose sodium, magnesium stearate, polyvinyl alcohol, polyethylene glycol, titanium dioxide, talc, and FD&C blue #2/indigo carmine aluminum lake. LANRA tablets are packaged in white, high-density, polyethylene bottles with silica gel desiccant and polyester packing material. Each bottle is enclosed with a white, continuous thread, child-resistant screw cap with an induction sealed liner. LANRA tablets should be stored at a controlled room temperature of 15°C to 30°C (59°F to 86°F). Storage conditions are specified on the label. To ensure the stability of LANRA tablets, the drug product should not be dispensed into a container other than that in which it is supplied. Measures that minimize drug contact with the body should always be considered during handling, preparation, and disposal procedures. Appropriate precautions should be followed to avoid direct eye contact or exposure through inhalation when handling LANRA. If eye contact does occur, affected areas should be washed with a large amount of water.

**In Phase 1b**, administer LANRA *without gilteritinib* on Cycle 1, Day 1. Beginning on Day 2 of Cycle 1, co-administer LANRA tablets with gilteritinib once daily at approximately the same time each day, with 8 ounces (240 mL) of water. **In Phase 2**, patients should initiate treatment with both LANRA and gilteritinib on Cycle 1, Day 1.

Patients who have a delay of < 12 hours should take the planned dose as soon as possible after the intended time of administration. For patients who have a delay of ≥ 12 hours, the missed dose should not be taken. Return to the normal schedule the following day. Do not

CONFIDENTIAL

Protocol KB-LANRA-1001 v7.0 Global  
(Amendment 6.0 Global)

administer 2 doses within 12 hours of each other. Vomited doses should not be repeated except if the tablets are clearly visible in the vomitus.

LANRA may be taken in either the fed or fasted state and with or without acid reducing agents, including PPIs.

## 8.0 Treatment Modifications

Treatment interruptions and dose reductions for management of toxicities as described below are permitted at any time. In general, patients who experience Grade 1 or 2 toxicities should continue treatment without interruption or dose reduction, if these are manageable with supportive care interventions.

### 8.1 Non-hematologic toxicities

#### 8.1.1 Gilteritinib

**Table 2: Treatment Modifications for Gilteritinib-Associated Toxicities**

Differentiation Syndrome (DS)*:	
 
• If DS is suspected, administer systemic corticosteroids (IV dexamethasone, 10 mg every 12 hours or equivalent) for a minimum of 3 days and initiate hemodynamic monitoring until symptom resolution.
 
• Interrupt gilteritinib if severe signs and/or symptoms persist for more than 48 hours after initiation of corticosteroids.
 
• Resume gilteritinib at full dose when signs and symptoms improve to Grade <math>\leq 2</math>.
 

Posterior reversible encephalopathy syndrome (PRES)**:	
 
• Discontinue gilteritinib.
 

QTcF interval greater than 500 msec:	
 
• Follow instructions provided in Section 11.7.3 regarding follow-up ECG assessments at the time of the event.
 
• Interrupt gilteritinib.
 
• Resume gilteritinib at 80 mg/day when QTcF interval returns to within 30 msec of baseline or <math>\leq 480</math> msec.
 

QTc interval increased by $>30$ msec on Day 8 of Cycle 1 compared to baseline:	
 
• Confirm with repeat ECG on Day 9.
 
• If confirmed, consider dose reduction to 80 mg/day.
 

Pancreatitis:	
 
• Interrupt gilteritinib until pancreatitis is resolved.
 
• Resume gilteritinib at 80 mg/day.
 

Liver function abnormalities:	
 
• For Grade 1-2 abnormalities, continue gilteritinib at full dose.
 
• For Grade <math>\geq 3</math> AST, ALT elevations interrupt gilteritinib and re-check
 

	
values at least weekly. If AST, ALT elevations resolve to Grade 1 or baseline in <math>\leq 14</math> days, re-start gilteritinib at 80 mg/day.
 
 
• Permanently discontinue gilteritinib for Grade <math>\geq 3</math> total bilirubin, interruptions lasting <math>> 14</math> days or recurrence of Grade <math>\geq 3</math> AST, ALT elevations despite dose reduction.
 

Diarrhea:	
 
• For Grade 3 diarrhea, uncontrolled with anti-diarrheal medications, interrupt gilteritinib until diarrhea resolves to Grade <math>\leq 1</math>.
 
• Re-start at 80 mg/day if resolved after interruption lasting <math>\leq 14</math> days. If Grade 3 diarrhea does not recur after 2 weeks of reduced dose gilteritinib, escalation to full dose may be attempted at investigator's discretion.
 
• Permanently discontinue gilteritinib for Grade 4 diarrhea, interruption lasting <math>> 14</math> days or recurrence of Grade 3 diarrhea despite dose reduction.
 

Other Grade $\geq 3$ toxicity related to gilteritinib † :	
 
• Interrupt gilteritinib.
 
• Upon recovery to Grade <math>\leq 1</math> or baseline in <math>\leq 14</math> days after interruption, resume gilteritinib at 80 mg/day. For interruptions lasting <math>> 14</math> days or recurrence of Grade <math>\geq 3</math> toxicity despite dose reduction, permanently discontinue gilteritinib.
 

\*DS is associated with rapid proliferation and differentiation of myeloid cells and may be life-threatening or fatal if not treated. Symptoms of DS include fever, dyspnea, pleural effusion, pericardial effusion, pulmonary edema, hypotension, rapid weight gain, peripheral edema, rash, and renal dysfunction. Some cases may present with concomitant acute febrile neutrophilic dermatosis. DS may occur as early as 2 days and up to 75 days after gilteritinib initiation and has been observed with or without concomitant leukocytosis.

\*\*A diagnosis of PRES requires confirmation by brain imaging, preferably magnetic resonance imaging (MRI).

†Since patients will be receiving study treatment daily, chronic, low grade side effects, such as nausea, fatigue, mucositis and diarrhea, while not meeting criteria for treatment modifications, may not be tolerable when experienced for long periods of time. Dose reduction for chronic, low-grade toxicities attributed to gilteritinib may be permitted if these cannot be managed effectively with supportive care.

Patients who are intolerant of the study regimen beyond Cycle 1 may either permanently discontinue one or both study medications or interrupt study treatment in consultation with the medical monitor until the toxicity or laboratory abnormality has resolved to Grade 1. For additional details regarding modification of gilteritinib treatment for toxicities, consult the local prescribing information.

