### 11.7.3 Cardiac function and ECG

Obtain triplicate ECG measurements, each separated by approximately 2 minutes with the patient in semi-recumbent position at the following time points in **Phase 1b**: Screening, on Days 1 (predose), 8 (pre- or post-dose) and 15 (predose) of Cycle 1, Day 1 of Cycle 2 and Cycle 3 (both pre- or postdose). **On Cycle 1, Day 1 and Cycle 1, Day 15, additional triplicate ECGs paired with PK blood samples are required at Hours 1, 2, 4 and 6 post-dose (see Table 8 and Table 9)**. In **Phase 2**, obtain triplicate ECG measurements at Screening, Cycle 1 Day 8, Cycle 1 Day 15, Cycle 2 Day 1, and Cycle 3 Day 1 (all pre- or post-dose).

All ECG recordings will be performed using a high-quality, high-fidelity digital electrocardiograph and centrally reviewed and interpreted. To minimize postural variability, ECG recordings must be obtained after the patient has been resting in a semi-recumbent position for at least 10 minutes. When coinciding with blood draws or other procedures (eg, vital sign measurements), ECG assessments should precede these. Environmental factors that may induce changes in heart rate (eg, television, radio, etc.) should be avoided as much as possible.

For safety monitoring purposes, the investigator or his/her designee should review, sign and date all ECG tracings with paper copies kept as part of the patient's permanent study file at the site. Digital recordings of ECGs sent to the central reading facility will be stored in a repository under the supervision of the reading facility or with the sponsor/designee. If QTc interval prolongation is observed (mean QTcF > 500 msec and/or >60 msec longer than baseline) during study treatment, another triplicate ECG must be obtained within the next 5 minutes. If confirmed on repeat triplicate ECG, an unscheduled PK sample should be collected ([Section 11.5](#)) and follow-up ECGs recorded at least hourly, until the prolongation is reversed or stabilized, or the

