investigator determines that there is no significant arrhythmic risk. Other possible causes for QTc prolongation should be investigated including electrolyte abnormalities, concurrent medication use known to prolong QT interval, etc. The medical monitor should be notified, and a decision made whether to discontinue study treatment. **See Table 2 for gilteritinib treatment modification in the setting of QTcF interval prolongation to > 500 msec at any time and/or a >30 msec increment on Cycle 1, Day 8 compared to baseline.**

The sponsor will evaluate the relationship between LANRA PK parameters and ECG intervals on an on-going basis and may modify the schedule of Cycle 1, Day 1 PK/ECG paired assessments based on updated information during the study.

An assessment of left ventricular ejection fraction will be performed at Screening and as clinically indicated during the treatment phase. An ECHO or MUGA scan is acceptable.

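### Table 2's rule for restarting gilteritinib after QTcF >500 msec has no ceiling on its relative limb: at baselines of 471 to 480 msec it is met between 501 msec and baseline + 30 (at most 510), still inside the stop trigger

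*Protocol*

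**What the plan says.** The relevant row of Table 2 (Protocol Section 8.1.1) is headed "QTcF interval greater than 500 msec". It sends the site to Section 11.7.3 for follow-up ECGs, interrupts gilteritinib, and then gives the restart rule: "Resume gilteritinib at 80 mg/day when QTcF interval returns to within 30 msec of baseline or" at most 480 msec.

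Eligibility sets the range of baselines. Exclusion criterion 10 in Section 5.2 removes "Patients with a corrected QT interval (using the Fridericia formula, QTcF) >480 msec or Long QT Syndrome", so a QTcF of exactly 480 msec is admissible.

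Two other texts bear on the restart decision:

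- **Section 11.7.3** requires a repeat triplicate when mean QTcF exceeds 500 msec. If prolongation is confirmed, it requires a PK sample and "follow-up ECGs recorded at least hourly, until the prolongation is reversed or stabilized", or until the investigator sees no significant arrhythmic risk. It adds: "The medical monitor should be notified, and a decision made whether to discontinue study treatment". For dosing it points back: "See Table 2 for gilteritinib treatment modification in the setting of QTcF interval prolongation to > 500 msec at any time".
- **The text after Table 2** allows patients who do not tolerate the regimen after Cycle 1 to "interrupt study treatment in consultation with the medical monitor until the toxicity or laboratory abnormality has resolved to Grade 1". It closes with "For additional details regarding modification of gilteritinib treatment for toxicities, consult the local prescribing information".

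**The concern.** A restart criterion should describe a state the patient reaches after leaving the one that caused the hold. Here the absolute limb does that and the relative limb need not. When baseline is already long, adding 30 msec carries the permitted restart value past 500 msec, and one reading then meets both the instruction to hold and the condition for restarting.

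This falls on the patients admitted with the longest QTcF. The protocol reports QT prolongation in 9% of patients on gilteritinib (Section 2.5.1) and describes lanraplenib's own potential as unknown (Section 10.2 and Appendix 4). What is at stake is the safety of a dosing instruction, not a statistical property of the trial.

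**Working it through.** **Inputs**

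- Stop trigger: QTcF > 500 msec (Table 2, row heading).
- Restart: QTcF − baseline ≤ 30 msec, or QTcF ≤ 480 msec (Table 2, third bullet of the row).
- Highest admitted QTcF: 480 msec (Section 5.2, criterion 10).

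The plan states no figure to reproduce.

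**Formulas**, in whole msec, with b the baseline:

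- Restart limit as written = max(480, b + 30).
- Overlap with the stop trigger = max(0, limit − 500).
- Restart limit with a 500 msec ceiling on the relative limb = max(480, min(b + 30, 500)).

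| Baseline b | Limit as written | Overlap | Limit with ceiling |
|---|---|---|---|
| 450 | 480 | 0 | 480 |
| 460 | 490 | 0 | 490 |
| 470 | 500 | 0 | 500 |
| 471 | 501 | 1 | 500 |
| 473 | 503 | 3 | 500 |
| 475 | 505 | 5 | 500 |
| 478 | 508 | 8 | 500 |
| 480 | 510 | 10 | 500 |

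This gives three zones. Up to 450 msec the limit is 480. From 451 to 470 the relative limb is the looser of the two, with limits of 481 to 500, but it stays clear of the trigger. From 471 to 480 it crosses into the trigger. The ranges are paired: each baseline has its own band, from 501 to b + 30, and only a baseline of 480 has the whole of 501 to 510.

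**Strict reading.** If within 30 msec means less than 30, the relative limit becomes b + 29. Then 471 gives 500 (no overlap), 472 gives 501 (1 msec) and 480 gives 509 (9 msec). The overlap covers baselines 472 to 480.

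**Example.** Baseline 478, peak 515, later reading 507. The later reading is 507 − 478 = 29 msec above baseline, so the relative limb is met on either reading, while 507 is still above 500.

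**Does another text supply the ceiling?** Section 11.7.3 requires review but gives no restart value, and it refers back to Table 2. Its hourly ECGs may end on stabilization or on the investigator's judgement, and neither is tied to 500 msec. The text after Table 2 is permissive and applies beyond Cycle 1, whereas the Phase 1b ECGs on C1D1, C1D8 and C1D15 fall inside Cycle 1. The prescribing information is not part of the documents.

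**Baseline definition.** Table 2 does not define baseline. SAP Section 4.4.4 uses the mean of the C1D1 predose triplicate, and no recheck of criterion 10 on C1D1 is stated. If that value guided dosing and exceeded 480 msec, the overlap would be wider than shown.

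**The case against.** The strongest reply is that the row can be read without conflict. The heading governs: above 500 msec the drug is held, with no exception for long baselines, and the restart bullet speaks of QTcF returning to a recovered level. On that reading a patient at 507 msec stays off drug.

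The relative limb also looks deliberate. Table 2 uses recovery to baseline as an alternative test for transaminases and other toxicities, and the next row acts only on a rise of more than 30 msec on Cycle 1 Day 8. Section 11.7.3 then puts the case before the medical monitor, restart is at 80 rather than 120 mg/day, and Section 10.2 prohibits drugs with known QT risk. Finally, the wording may follow the label, which cannot be checked here.

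Much of this stands as a limit on the risk: a restart above 500 msec would be neither automatic nor likely. A baseline-relative test is also a reasonable recovery criterion. It does not remove the inconsistency. A return implies a fall from a higher value, not a fall below 500, and none of the safeguards gives a number. The amendment keeps the relative limb and only stops it from being met inside its own stop trigger.

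**Conclusion.** The concern holds, as a minor one. For baselines of 471 to 480 msec, Table 2 permits restart at readings where the same row requires interruption, over a band 1 to 10 msec wide (472 to 480 msec and 1 to 9 msec on the strict reading). The ranges assume that the baseline used for dosing is no higher than 480 msec.

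Only patients in that band who exceed 500 msec on treatment and are then considered for restart are affected. The documents give no count, and I expect the subset to be very small. No endpoint, sample size or error rate depends on it.

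**What to change.** Replace the third bullet of the row with: *Restart gilteritinib at 80 mg/day once QTcF is ≤480 msec, or is within 30 msec of baseline and in any case ≤500 msec.*

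This removes the overlap at every admitted baseline. The limit is unchanged for baselines of 470 msec or less and falls by 1 to 10 msec for 471 to 480, so the clinical cost is a slightly longer hold for a few patients. It is a one-line edit with no added visits, ECGs or SAP changes. The wording should be checked against the local prescribing information when it is made.

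SAP Section 7 records that the sponsor terminated the trial at completion of Phase 1b and that Phase 2 was not enrolled. The edit therefore helps only any Phase 1b patient still taking gilteritinib (the documents do not say whether there are any) and any later protocol that reuses the table.
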